involved in recognizing mental health outcomes that may take 1-2 decades to be detected complicates investigations further. As ART regimens evolve, monitoring for HEU outcomes will remain important. Maternal HIV prevalence is >20-30% in some regions of sub Saharan Africa, which means that a substantial proportion of *all* children/adolescents have fetal exposure to HIV/ART, which may have long-term impact on developmental outcomes. Ideally, well conducted studies could provide reassuring data of limited risks from fetal HIV/ART exposure. Detecting epidemiologic signals for links between fetal HIV/ART exposure and mental health outcomes is important to inform our understanding of biologic or psychosocial determinants of adolescent mental health both among HEU and in general. If there are risks, regimens and psychosocial interventions could be tailored to decrease these risks as mechanisms are better understood and children at risk could be identified for early intervention.

[figure not shown]
9. Literature review

Parallel longitudinal cohorts and population-based cross-sectional groups combined in a virtual cohort will provide an innovative and efficient approach to evaluate HEU from infancy to adolescence, assessing short- and long-term outcomes. Our proposed cohorts span urban and rural settings and span HEU/HUU from 6 weeks to 18 years with adequately powered age strata to discern differences in mental health outcomes. This deep and broad assessment is novel and will provide distinct cohorts in which to demonstrate epidemiologic consistency in findings regarding HEU risk and cofactors. Parallel study designs provide complementary strengths – the longitudinal infant cohort with universal Option B+ coverage and homogeneous age at recruitment provides clear ascertainment of perinatal HIV/ART exposure and early outcomes with minimal bias; this cohort will provide timely data as DTG use expands and could be extended past the study period. The older cross-sectional cohort may reveal associations of fetal HIV/ART exposure with mental health outcomes that are not detectable in early childhood. Multiple cohorts strengthen causal inference – by including longitudinal and population-based surveys, short- and long-term outcomes, and nested case-control studies – we can strengthen causal inference by demonstrating *consistency* between studies.

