Fine Motor (N=47)	-1.02	0.38	0.007
Social (N=46)	-0.55	0.13	0.4
Language (N=48)	-0.89	-0.19	0.06

*Paired T test, Malawian norm

has conducted detailed studies on neurocognition in school-aged children. **To evaluate neurodevelopment in infants and young children, we trained clinical officers to administer the Malawi Developmental Assessment Tool (MDAT)**¹⁰⁴ at community health clinic and hospital study sites in Kenya. We found that following ART initiation, PHIV <5 years old had significant improvements in gross and fine

motor domains, a trend for improvement in language, but no gain in social functioning (Table 2).¹⁰⁵ These data demonstrate our ability to conduct neurodevelopmental assessments in children. **[name] has established capacity for cognitive assessments in Kenya.** As part of her K01 award, [name] received guidance and training from Drs. [name] (MSU) and [name] (Makerere University) to build capacity for cognitive assessments. The assessment battery included the Kaufman Assessment Battery for Children, 2nd ed. (KABC), the Test of Variables of Attention (TOVA), the Behavior Rating

Table 3. Differences in cognitive and motor ability for HEU (N=58) vs HUU (N=61) school-aged children

Neurocognitive domain (Assessment)	Adj. z-score difference
Cognition (KABC)	-0.3*
Short-term memory (KABC)	-0.4**
Processing speed (TOVA)	-0.9**
Visual-spatial (KABC)	-0.2
Attention (TOVA)	-0.2
Executive functioning (BRIEF)	-0.3
Motor (BOT-MP)	-0.3*

Note, HUU, HIV-unexposed; Raw scores standardized using US norm. *p ≤0.05; ** p≤0.005

Inventory of Executive Function (BRIEF) and the Buterinks Oseretsky Test of Motor Proficiency , 2nd ed. (Brief Form) (BOTMP)¹⁰⁶⁻¹⁰⁸. **We found significant deficits in HEU children in memory, processing speed and motor scores, compared with HUU children**, in analyses adjusted for socioeconomic indicators including caregiver education, household monthly rent and food security (Table 3). **These studies illustrate our expertise in neurodevelopmental assessments in Kenya, including with HEU and HUU, and demonstrate that HEU may have cognitive delays compared to HUU.**

[figure not shown]

Figure 4. CHIME study teams visited 141 clinics throughout Kenya

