Screening for child mental health conditions. The Strengths and Difficulties Questionnaire¹³¹ is a 25-item scale widely used as a screening tool for mental health in numerous LMIC settings¹³², including SSA¹³³. The SDQ will be used beginning at age 3. The SDQ includes 4 difficulty scales (emotional symptoms, conduct problems, hyperactivity/inattention, and peer relationship problems) and a scale for prosocial behavior. The Strengths and Difficulties Questionnaire¹³¹ is a 25-item scale widely used as a screening tool for mental health in numerous LMIC settings¹³², including SSA¹³³. The SDQ will be used beginning at age 3. The SDQ includes 4 difficulty scales (emotional symptoms, conduct problems, hyperactivity/inattention, and peer relationship problems) and a scale for prosocial behavior. SDQ scales had good internal consistency in African studies¹³⁵⁻¹³⁹, although the hyperactivity/inattention scale has performed less well¹³⁸. Poor SDQ scores correlated with expected demographic characteristics in South Africa and Uganda¹³⁷. A z-score corresponding to the 80th-90th and >90th percentiles have been considered borderline and indicative of 'caseness'¹³⁶, and will prompt further screening.

Hearing: We will use combined otoacoustic emission (OAE) and auditory brainstem response (ABR) screening tests to assess hearing. Infants will be screened at 6 weeks using OAE and referred for ABR if they screen positive. At age 3 and 4 years, we will use a smart phone based hearing screen (Hearscreen TM) to assess hearing. These tests are non-invasive and does not involve input of energy into the body.

Summary table for aim 1 data collection

	Enrollment	Month 6	Month 12	Month 18	Month 24	Month 30	Month 36	Month 42	Month 48
Consent	X								
Locator data	X	X	X	X	X	X	X	X	X
Medical history	X	X	X	X	X	X	X	X	X
Anthropometry	X	X	X	X	X	X	X	X	X
MDAT	X	X	X	X	X	X	X	X	X
SDQ							X	X	X
ASD screen				X	X				X
Hearing screen	X						X		X
DBS	X		X		X		X		X

vii. Sample size determination & data analysis

For **all analyses**, *a priori* cofactors of interest in the multivariate analysis include household sociodemographic factors, birthweight, preterm birth, maternal depression, infant sex, maternal education, and infant/child LAZ. Collinearity will be examined using standard error assessments and multivariate models will include non-collinear variables associated with growth in univariate model ($p < 0.05$).

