R33 Aim 2				
Difference in BENC1 scores	0.29	1000 HEU: 100 HUU age stratum (7-11yo)		SD=1.0
Difference in ADHD prev.	7.7%	1000 HEU: 100 HUU		2.7% in HUU ¹⁷⁵
Difference in depression prev	10.1%	1000 HEU: 100 HUU per age stratum		HUU 10%

Analyses: For binary outcomes such as ADHD and depression, multivariate generalized linear models (GLM) with log link and binomial family for relative risk estimation clustered by site will be used. For continuous variables such as NIH-Toolkit, we will use multivariate GLM with Gaussian family and identity link. As previously noted in Aim 1, we will include *a priori* potential confounders - maternal depression, preterm birth, and infant birthweight - in multivariate analysis, after assessment of collinearity.

MDAT (social, fine motor, gross motor, language)	GLM
Hearing	GLM
BENCI (processing speed, visual-motor coordination, attention, language, memory, executive function)	GLM
SDQ total domain score	GLM
ADHD screen (analyze positive SNAP-IV and subset validated on MINI-Kid)	GLM
PHQ-9 (prevalence of moderate-severe symptoms)	GLM
Neuropsychiatric diagnoses	GLM

Training procedures for aim 1 and 2

The study team will develop protocols and training materials for clinic staff. A 5-day training workshop will be designed. The package will include the basics of early childhood development, pediatric mental health, screening and use of the study screening and diagnostic tools. The training will cover neurodevelopmental assessments, psychometric testing, and administration, scoring and interpretation of the MDAT and NIH Toolbox. The 5-day nurse training workshop will cover general sensitization to the testing situation, including ensuring that the child follows the instructions, methods of cross-checking to determine whether a child understood instructions, learning when to give breaks, how to re-engage the child and how to react to distress. The training will cover how to recognize need for referrals and provide motivational interviewing and culturally sensitive assessment skills. To ensure quality control, the study coordinator will conduct refresher training for staff to ensure operating procedures are followed consistently. We will also develop checklists for tests requiring multiple tests as well as the use of tablet based tests to ensure quality assessments.

e. Aim 3

i. **Study design**

This Aim of the study involves 2 cross-sectional components:

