Pitfalls and alternative strategies: The Aim 1 cohort is designed to be homogeneous – with all HEU having initiated ART either before or during pregnancy and all enrolled contemporaneously at 6 weeks of age, which accommodates secular trends in comparisons with the HUU cohort. HUU will be recruited from the same MCH clinic as HEU, which ensures that mothers reside in the same community, and thus have similar sociodemographic characteristics; this attenuates risk for confounding in comparisons between HEU and HUU. We will not enroll during pregnancy, which will under-ascertain perinatal morbidity and preterm birth. However, we have access to 3 ongoing birth cohorts that are accruing pregnancy-enrolled HEU and HUU. Data from those cohorts complement this study, which is designed to be a population-based multi-site urban/rural cohort.

17. Timeline

Timeline: In the first 6 months we will obtain study approval, recruit and train staff and establish study sites. We anticipate to complete enrollment for the longitudinal cohort in the second half of year 1. Aim 2 pilot will begin in the second half of year 1 and be complete in 10 months. Aim 2 population surveys will begin after the pilot in the second half of year 2. Aim 3 activities will be conducted in year 4-5.

Study Timeline					
	Year 1	Year 2	Year 3	Year 4	Year 5
Study approvals, training	■				
Aim 1 Enroll longitudinal cohort		■			
Follow-up longitudinal cohort		■	■	■	■
Aim 2 Pilot cross-sectional cohort		■	■		
Aim 2 Population based assessments			■	■	
Aim 3 Cost analysis				■	■
Aim 3 Stakeholder meeting					■

18. Human subjects

a) Ethical Approval

We will obtain ethical approval from the University of Washington (UW) Human Subjects Division (IRB) and Kenyatta National Hospital-University of Nairobi (KNH-UoN) Ethics and Research Committee (ERC). There will be minimal risk to the participants taking part in this study. Any changes to the protocol will be submitted to the UW IRB and KNH-UoN ERC.

b) Collaborating sites

The study will be conducted in collaboration with the UW, KNH, and UoN. The study will be reviewed by the KNH ERC and UW IRB and will not be started before approvals are obtained from all two organizational review boards.

c) Informed Consent

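### The Aim 2 confounder list claims to repeat the Aim 1 list but names no socioeconomic factor, and the Aim 1 text it points to would not secure socioeconomic adjustment either

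*Protocol*

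**What the plan says.** The covariate sentence of the Aim 2 analysis paragraph (Protocol section 12.d.vii, Analyses) begins: "As previously noted in Aim 1, we will include *a priori* potential confounders - maternal depression, preterm birth, and infant birthweight". From the list to its end it reads: "potential confounders - maternal depression, preterm birth, and infant birthweight - in multivariate analysis, after assessment of collinearity". Three variables stand between dashes, with no word to show that they are examples.

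The Aim 1 text it refers to (section 12.c.vii) opens "For all analyses, *a priori* cofactors of interest" and names seven entries: "cofactors of interest in the multivariate analysis include household sociodemographic factors, birthweight, preterm birth, maternal depression, infant sex, maternal education, and infant/child LAZ". The next sentence adds a selection rule: "multivariate models will include non-collinear variables associated with growth in univariate model", at p < 0.05.

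On recruitment, section 12.d.iii finds HEU through caregivers attending HIV clinics. HUU are found through household visits by nurses and community health workers in the area around the same clinic. Section 11 matches the 400 HUU of Aim 2b on age stratum. Section 16 argues that recruiting both groups from one MCH clinic makes the mothers similar and that "this attenuates risk for confounding in comparisons between HEU and HUU". That paragraph is about the Aim 1 cohort; no counterpart is given for Aim 2. Section 12.d.vi has sociodemographic information collected from Aim 2 caregivers.

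**The concern.** The second list presents itself as the first one repeated, yet four of the seven entries are gone. Among them are the two that carry socioeconomic position: household sociodemographic factors and maternal education. An analyst who follows the Aim 2 sentence as written fits a different model from one who follows the Aim 1 sentence.

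The choice matters more in Aim 2 than in Aim 1. A mother in HIV care and a mother visited at home may differ in education or household means, and matching on age stratum does nothing about that. Clustering by site, which the plan states for the binary outcomes, deals with correlation within a site and not with differences between individual households. Any such difference that also affects cognition or mental health would be read as an effect of fetal HIV or ART exposure. The team's own earlier HEU-HUU cognitive comparison (section 9, preliminary data) reports "analyses adjusted for socioeconomic indicators including caregiver education, household monthly rent and food security", so it thought the control worth having.

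The protocol also wants the two aims to "provide distinct cohorts in which to demonstrate epidemiologic consistency in findings regarding HEU risk and cofactors". Agreement or disagreement between them is harder to interpret if it may come from different adjustment sets.

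**Working it through.** **1. The two lists side by side.**

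| Variable | Aim 1 list (12.c.vii) | Aim 2 list (12.d.vii) |
|---|---|---|
| Maternal depression | yes | yes |
| Preterm birth | yes | yes |
| Birthweight | yes | yes |
| Household sociodemographic factors | yes | no |
| Maternal education | yes | no |
| Infant sex | yes | no |
| LAZ | yes | no |

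**2. What each reading gives.**

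- Literal reading: the Aim 2 models hold three covariates, none of them socioeconomic.
- Reference-back reading: all seven are candidates, but the Aim 1 rule retains those related to growth at p < 0.05. Growth is measured in Aim 2, but it is not in the Aim 2 analysis table, which covers MDAT, hearing, cognition, SDQ, ADHD, PHQ-9 and neuropsychiatric diagnoses. A variable that predicts cognition or depression but not growth would be dropped.

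**3. The protocol's yardstick.** The effect-size table gives a detectable difference of 0.29 in the Aim 2 cognitive score for 1000 HEU and 100 HUU per stratum, SD 1.0. Power of 80% and alpha of 0.05 are stated for Aim 1; I assume the same, two-sided, for Aim 2.

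- SE = sqrt(1/100 + 1/1000) = 0.1049
- Detectable difference = (1.960 + 0.842) × 0.1049 = 0.294
- Power at 0.29 is 79.0%, so the stated figure is reproduced.

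**4. Illustration of the stake.** The documents give neither input below; both are assumptions. Complete omission of socioeconomic factors is also assumed, with no indirect control through the three named variables and no allowance for clustering.

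- HEU-HUU socioeconomic gap: 0.2 to 0.5 SD
- Outcome slope: 0.1 to 0.3 SD per SD of socioeconomic position
- Bias = gap × slope
- False-positive rate = Φ(−1.96 + bias/SE) + Φ(−1.96 − bias/SE)

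| Gap | Slope | Bias (SD) | Share of 0.29 | Bias/SE | False-positive rate, 1000:100 |
|---|---|---|---|---|---|
| 0.2 | 0.1 | 0.02 | 7% | 0.19 | 5.4% |
| 0.3 | 0.2 | 0.06 | 21% | 0.57 | 8.8% |
| 0.5 | 0.2 | 0.10 | 34% | 0.95 | 15.9% |
| 0.5 | 0.3 | 0.15 | 52% | 1.43 | 29.8% |

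**The case against.** The tempting stronger reading is that Aim 2 compares HEU with HUU without any socioeconomic control. The documents do not support that. The Aim 2 sentence points back to Aim 1, and the Aim 1 list is introduced as applying to all analyses, so the three names may be shorthand. Nothing says that socioeconomic factors are excluded. HUU also come from the neighbourhood of the same clinic, which gives some control by design, much like the shared-community argument made for Aim 1.

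This removes the stronger claim but not the point. Where the Aim 1 section shortens its list for the SDQ analysis, it keeps sociodemographic factors. Where the telomere analysis carries the list over whole, it says so. The Aim 2 sentence does neither. One could also argue that the growth screen was meant for additional variables only and that the a priori set is always kept. The text makes no such exemption.

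Three further limits stand:

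- The preliminary study shows only that socioeconomic adjustment was made. No unadjusted result is given, so it is not evidence that confounding was material.
- Pooling all strata (4000:400, SE 0.0524) takes the false-positive rate to 82% at the largest assumed bias. A reader should not adopt that as the expected size: it pairs the worst case with a standard error that ignores site clustering, while the protocol sizes Aim 2 per stratum.
- The consistency argument spans deliberately different designs and ages and does not promise identical adjustment. Aim 1 adjustment is subject to the same growth screen, so it is no secure benchmark either.

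**Conclusion.** The point holds as an inconsistency with a practical consequence. The two a priori lists differ although the second claims to follow the first, and on neither reading does the text secure socioeconomic adjustment of the Aim 2 HEU-HUU estimates. It does not show that those estimates will be confounded.

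The size cannot be taken from the documents. Under the assumed inputs and complete omission, the bias runs from negligible (0.02 SD, false-positive rate 5.4%) to about half the detectable difference (0.15 SD, 29.8%) in a 1000:100 stratum. The point concerns the HEU-HUU comparisons; simple estimates of burden within HEU do not depend on this list. It should be corrected because the correction is cheap and the two groups are recruited by different routes.

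**What to change.** In section 12.d.vii, replace the partial restatement with one explicit Aim 2 list. To the three variables already named, add household socioeconomic indicators, maternal education, child sex and child age. State that these enter every HEU-HUU model regardless of the growth-based p < 0.05 screen. Make the same list and the same exemption apply to the matching Aim 1 models in section 12.c.vii.

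Name the household indicators from what the Aim 2 questionnaire collects. Section 12.d.vi promises sociodemographic information without itemising it, so rent and food security should be listed only if they are in the form. Child sex is there mainly for precision, since it is not a plausible cause of maternal HIV status.

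Keep maternal depression, preterm birth and birthweight unless their removal is argued separately. Section 8 presents poor fetal growth and maternal depression in pregnancy as possible routes to HEU outcomes, so whether to adjust for them is a separate question that this change need not settle.

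The cost is one or two sentences and a few extra model terms. No new data collection is needed if the indicators are drawn from the existing questionnaire.

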This study will provide rigorous epidemiologic evidence regarding the influence of fetal exposure to HIV and ART on developmental and mental health outcomes from infancy to adolescence, including obtaining a national population-based estimate of HEU burden of developmental and mental health outcomes and strategies for programmatic surveillance and referral.

11. Specific aims and hypotheses

Aim 1: Within a longitudinal cohort of 1000 HEU and 1000 HUU infants enrolled at 6 weeks of age from 5 MCH clinics and followed 6-monthly:

HOPE study protocol

Version 1.3

July 21, 2020

Aim 1a. To compare HEU and HUU infants and children for growth, hearing, and neurodevelopmental outcomes; and determine influence of ART timing/regimen on HEU outcomes. To determine whether fetal HIV/ART exposure impacts 4-year neurodevelopmental outcomes; and assess impact of peripartum ART regimen and timing.

Aim 1b: To compare telomere length in HEU and HUU and determine associations with neurodevelopmental outcomes.

Aim 2a: To determine the impact of HEU and HUU status, as well as maternal peripartum ART, on neurodevelopment and mental health (ASD, ADHD, depression, and anxiety). We will pilot a mobile screening strategy to detect adverse neurodevelopmental and mental health outcomes in HEU for use in large-scale screening in Aim 2b. Mothers attending HIV care will be invited to bring their HEU (aged 3-18) (200 HEU, 50 per age-stratum: 3-6, 7-10, 11-14, 15-18) for screening; age- matched HUU will be recruited from the community.

Aim 2b. To estimate population-burden and cofactors of adverse neurodevelopmental and mental health outcomes in HEU using mobile teams to screen HEU in ~100 large HIV Care Clinics throughout Kenya (4000 HEU; age-stratified, 3-6, 7-10, 11-14, 15-18) and 400 age-stratum matched community HUU.

Aim 3. To estimate the cost of this screening strategy and convene stakeholders to review data regarding programmatic integration of HEU screening.

12. Study design and methodology

a. Study area description

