Cross-sectional surveys. These will be done in 2 phases 1) Pilot phase and 2) Population phase. The pilot phase will be conducted in one facility (Rachounyo sub-County hospital) after which we will begin population based assessments in 100 large HIV clinics. Procedures for enrollment and assessment are similar for 2 phases.

HOPE study protocol

Version 1.3

July 21, 2020

ii. Study populations

HEU and HUU caregiver-child pairs

iii. Recruitment procedures

MLHIV attending HIV Care clinics will be asked about potentially eligible HEU children aged 3-18 by study nurse. MLHIV who are interested in participating will be invited to return with their child/adolescent for participation in the study. Study nurses will also liaise with clinic community health workers (CHWs) to recruit eligible HUU in the relevant age strata (3-6, 7-10, 11-14, 15-18 years) in the community. CHWs will invite mothers of eligible HUU children to participate in the study for evaluation and mother-child/adolescent pairs will be enrolled at a neutral site (typically MCH or family planning [FP] clinic) or at home. Study nurses will be accompanied by the community health worker for home enrollments. A standard recruitment form will be used.

The target enrollment is 400 children and adolescents (200 HEU and 200 HUU) in the pilot phase and 4400 (4000 HEU and 400HUU) age 3-18 years (stratified to the following groups: 3-6, 7-10, 11-14, 15-18 and by HIV status (HEU or HUU)) in the population phase. The pilot phase will be conducted in one facility in rural Kenya (Rachuonyo Hospital HIV clinic), and the population phase in 100 large HIV care clinics with at least 1000 adult women in HIV care.

For HEU, caregivers attending HIV clinics who have children in the proposed age-groups will be recruited by the clinic staff. Caregivers who are interested will meet with the study nurse and be provided with details on the study and study procedures and invited to bring children for enrollment. All study procedures will be completed at enrollment with no follow-up procedures.

HUU will be recruited from the neighboring community around the HIV Care Clinic from where the HEU are recruited. Nurses and Community health workers (CHW) will visit households to recruit interested caregivers of children age 3-18 and enroll those who meet eligibility criteria and are willing to confirm HIV status (using HIV self-test kits) and enroll their children in the study.

Eligibility criteria

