Child mental health screening. The SDQ (described above) will be used to screen for mental health conditions in children through age 16 years. In 7-11 year old orphans in South Africa, the Parent SDQ had good construct validity with the Computerized Diagnostic Interview Schedule for Children -4th Ed. (CDISC-IV), with area under the curve (AUC) ranging from 0.73-0.82¹³⁸. In pre-school aged children the Total Difficulties Score (TDS; an aggregate) had 0.79 sensitivity and 0.93 sensitivity versus the Child Behavior Checklist¹⁴⁰. For older adolescents (>16 yrs), the PHQ-9 is a widely used screening test for depression validated in Ethiopia, Nigeria, Kenya and Uganda¹⁴¹⁻¹⁴³. In 15-40 year olds in Nigeria, the PHQ-9 had ≥ 0.85 sensitivity and 0.99 specificity for combined major and minor depressive disorders and major depression¹⁴⁴. We will administer SDQ to the child and with the parent (will respond to questions about their children).

Screening for ADHD. Because the SDQ may not optimally screen for ADHD, the SNAP-IV (revision of the Swanson, Nolan, and Pelham – SNAP) questionnaire will be administered to screen for ADHD^{145,146}. The Multimodal Treatment Study (MTA) version includes 26-items, has robust psychometric properties¹⁴⁵ and a caregiver/parent only approach has been used in South Africa¹⁴⁷. As in this South African study a score at the 95th percentile will be considered positive and will prompt further evaluation with the MINI-KID.

Diagnosis of neuropsychiatric disorders. The Mini International Neuropsychiatric Interview for children and adolescents (MINI-KID)^{148,149} is a diagnostic tool that included diagnosis of over 30 common pediatric psychiatric

HOPE study protocol

Version 1.3

July 21, 2020

morbidities among children and adolescents age 6-17 years, including depressive disorders, suicidality, anxiety disorders and ADHD.¹⁵⁰ The MINI-KID and the corresponding adult form (MINI) will be used to evaluate children and adolescents who screen positive on the SDQ or PHQ-9. Administration can take as little as 10 minutes by nurses and social workers¹⁵¹. The MINI-KID has been used in Nigerian and Ugandan adolescents age 10-19^{152,153}. Diagnosis of major depressive episodes using MINI-KID in Rwanda in 10-17 year olds aligned with local expression of depression-like symptoms¹⁵⁴.

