Cognitive outcomes. Cognitive assessments will be done using NIH Toolbox. The battery will include the tests Dimensional Change Card Sort Test, Flanker Inhibitory Control and Attention Test, List Sorting Working Memory Test, Pattern Comparison Processing Speed Test, and Picture Sequence Memory Test, which evaluate working memory, attention, processing speed, and other aspects of executive functioning. The NIH Toolbox has been validated for US children and was recently adapted through a rigorous process involving translation and backtranslation for Kenya, including translation to Dholuo and Kiswahili.

The table below summarizes the tools, age-group they are used in, screening time and domains or disorders they test.

Tool	Age-group	Time (minutes)	Types	Domains/Disorder
MDAT	0.6-5	30	Screening	Gross motor, fine motor, language, social
HearScreen TM	3+	5	Screening	Hearing
NIH Toolbox	6-17	25-30	Screening	working memory, attention, processing speed, executive functioning
Strengths and difficulties questionnaire (SDQ)	3-16 & caregivers	10	Screening	Emotional symptoms, conduct problems, hyperactivity/inattention, peer relationship problems
SNAP-IV	6-12	5-10	Screening	ADHD
PHQ-9	>16 & caregivers	3	Screening	Depression
MINI-KID	6-17	10	Diagnostic	Common psychiatric conditions
MINI	18	10	Diagnostic	Common psychiatric conditions
School performance	>10	1	NA	National exam results Parental report

vii. Sample size determination & data analysis

Effect size calculations: For comparisons of z-scores in MDAT or NIH-toolkit scores, we will be able to detect differences of 0.13-0.18 assuming a standard deviation of 1.0 or 1.4, 80% power and alpha of 0.05 in Aim 1 cohort (Table 10). In the cross-sectional cohort, 2- to 3-fold differences will be detectable, in diagnoses such as depression and ADHD. To detect smaller differences, more HUU could be enrolled in some age-strata based on pilot feasibility.

R61/R33 Aim 1 cohort	Effect detectable (no attrition)		Effect detectable (20% attrition)	Assumptions
Difference in z-score for MDAT	0.13 (SD=1.0)	1000 HEU:1000 HUU	0.14 (SD=1.0)	Standard deviation = 1.0-1.4 ¹⁰⁵
	0.18 (SD=1.4)		0.20 (SD=1.4)	
Difference in ASD prevalence	2.2%	1000 HEU:1000 HUU	2.5%	HUU ASD 2%
	3.3%	500 DTG: 500 EFZ	3.8%	
Difference in SDQ+ prev.	5.2%	1000 HEU:1000 HUU	5.9%	HUU SDQ+ 20%
	7.5%	500 DTG: 500 EFZ	8.5%	
Difference in hearing loss	1.7%	1000 HEU:1000 HUU	2.0%	HUU 1%
	2.7%	500 DTG: 500 EFZ	3.1%	
Difference in TL	0.18	500 HEU: 500 HUU		SD=1.0

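### Aim 2 compares HEU with HUU on PHQ-9 and SNAP-IV only as yes/no outcomes, so a doubling of ADHD or depression has low power that the scores already collected could probably raise

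*Protocol*

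**What the plan says.** The outcome table in section 12.d.vii (Aim 2) names "PHQ-9 (prevalence of moderate-severe symptoms" and "ADHD screen (analyze positive SNAP-IV and subset validated on MINI-Kid". The text above it treats ADHD and depression as binary and models them by log-binomial GLM clustered by site. The same table keeps the SDQ total and the cognitive domains as scores.

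For SNAP-IV, section 12.d.vi says that "a score at the 95th percentile will be considered positive" and uses the result to trigger the MINI-KID.

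The population phase plans "4400 (4000 HEU and 400HUU) age 3-18 years", in four age strata. The depression row of the effect-size table uses "1000 HEU: 100 HUU per age stratum", and the ADHD row has the same 1000 to 100. On what this can show, the protocol states: "In the cross-sectional cohort, 2- to 3-fold differences will be detectable, in diagnoses such as depression and ADHD".

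**The concern.** A cut-off suits referral and an estimate of burden. It is a costly choice for a group comparison when one group is small and the outcome uncommon. With 100 HUU, prevalences of 2.7% and 10% mean about 3 and 10 HUU events, and the yes/no analysis ignores all differences between children on the same side of the cut. The protocol gives no reason for treating these two tools differently from the SDQ and the cognitive battery.

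The background section hopes for reassuring data, and Aim 3 takes the evidence on HEU risk to policy makers. A null result from a comparison with little power for a doubling could be misread as reassurance.

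**Working it through.** **Inputs from the protocol.** 1000 HEU to 100 HUU; HUU prevalence 2.7% (ADHD) and 10% (depression); "80% power and alpha of 0.05 in Aim 1 cohort". I assume that the same alpha and power apply to the Aim 2 rows and that the test is two-sided.

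**Formula for the yes/no comparison.** With HUU proportion p0 and HEU proportion p1:
- p̄ = (100·p0 + 1000·p1)/1100
- SE0 = √[p̄(1−p̄)(1/100 + 1/1000)]
- SE1 = √[p0(1−p0)/100 + p1(1−p1)/1000]
- power = Φ[(p1 − p0 − 1.96·SE0)/SE1]

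**The plan's own figures first.** ADHD row, 2.7% plus 7.7 points = 10.4%: p̄ = 0.0970, SE0 = 0.0310, SE1 = 0.0189, power 80.4%. The row reproduces. It is a 10.4/2.7 = 3.85-fold difference, not 2- to 3-fold. The depression row (10.1 points) does not reproduce: the same formula gives 73% power there and needs about 11.0 points for 80%.

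**Doubling at 1000:100.**
- ADHD, 2.7% v 5.4%: p̄ = 0.0515, SE0 = 0.0232, SE1 = 0.0177, power 14.9%. A tripling (8.1%) has 48.9%.
- Depression, 10% v 20%: p̄ = 0.1909, SE0 = 0.0412, SE1 = 0.0326, power 72.2%.

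**Numbers who would take each tool.** The tool table in section 12.d.vi gives PHQ-9 to those over 16 and SNAP-IV to ages 6–12. The four strata span 16 years of age, so even ages (an assumption) give 400/16 = 25 HUU and 4000/16 = 250 HEU per year of age.
- PHQ-9 (17 and 18): 50 HUU, 500 HEU. Depression doubling: 37.8%.
- SNAP-IV (6 to 12, seven years): 175 HUU, 1750 HEU. ADHD doubling: 29.1%; tripling: 82.2%.
- If the 95th-percentile rule makes about 5% of HUU screen-positive, a doubling to 10% has 33.1% power at 1000:100 and 59.5% at 1750:175.

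**Power from the score.** The protocol gives neither distribution nor SD, so I show three cases.

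1. Normal score, pure location shift. The shift that doubles the proportion above the cut is d = z(1−p0) − z(1−2p0): 1.927 − 1.607 = 0.320 for ADHD and 1.282 − 0.842 = 0.440 for depression. Power = Φ(d/SE − 1.96), where SE = √(1/n_HUU + 1/n_HEU) is 0.1049 at 1000:100, 0.0793 at 1750:175 and 0.1483 at 500:50.
2. Right-skewed score: gamma, shape 0.5 to 2, with HEU scores scaled up until the proportion above the HUU cut doubles; comparison of means.
3. Tail only: an extra 2.7% or 10% of HEU move above the cut and nothing else changes. The mean shifts are 0.064 and 0.195 SD.

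| Doubling | Yes/no | Means, skewed | Means, normal | Means, tail only |
|---|---|---|---|---|
| ADHD, 1000:100 | 15% | 55–66% | 86% | 9% |
| ADHD, 1750:175 | 29% | 74–86% | 98% | 12% |
| Depression, 1000:100 | 72% | 94–98% | 99% | 45% |
| Depression, 500:50 | 38% | 73–77% | 84% | 26% |

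Rank tests gain less under skew. At 1000:100 they have about 29–53% for ADHD and 76–91% for depression.

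**Detectable score difference, 80% power.** (1.96 + 0.84)·SE = 0.29 SD at 1000:100, which matches the plan's cognitive row; 0.22 SD at 1750:175; 0.42 SD at 500:50.

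**The case against.** Four points can be made against this.

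- **The objectives name disorders.** Aim 2 lists ADHD and depression as conditions, and a mean symptom difference answers a different question from a relative risk of a disorder. This stands. It is a reason to keep the binary outcomes, not a reason to leave the scores out.
- **The score gain depends on its model.** A reader might take 86% and 99% as what the scores deliver. The documents do not support that: both figures need normal scores with a pure location shift, at 1000:100. Skew lowers the ADHD figure well below 86%, and a tail-only effect reverses the gain.
- **Maternal ART.** Aim 2a sets out "To determine the impact of HEU and HUU status, as well as maternal peripartum ART, on neurodevelopment and mental health", so a reader might infer that ART effects would also be missed. The shortage is of HUU, and the ART comparisons lie within the 4000 HEU. Under an assumed equal split in the tools' age ranges, the yes/no test already has about 82% power for an ADHD doubling (875:875) and 88% for a depression doubling (250:250). Aim 2a is also the pilot, with 200 HEU and 200 HUU; the powers above concern the population phase.
- **Partial cover elsewhere.** The SDQ total is analysed as a score up to age 16 and includes emotional and hyperactivity scales. However, the protocol itself doubts the SDQ for ADHD, and the PHQ-9 is used above the SDQ's age range. The protocol also allows more HUU in some strata, but fixes no number.

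**Conclusion.** The point holds for the HEU versus HUU comparison of depressive and ADHD symptoms. As planned, a doubling has about 15% power (ADHD) and 72% (depression) at the table's 1000:100, or about 29% and 38% in the tools' own age ranges. Only an ADHD tripling, with all ages 6–12 pooled, reaches about 82%. Comparing mean scores would probably raise power for a doubling to about 74–98% (ADHD) and 73–84% (depression) in those age ranges.

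This rests on two-sided 0.05, even ages within strata, the table's HUU prevalences, no allowance for site clustering (which would lower every figure), and an effect that moves more of the distribution than its extreme tail. It does not show that maternal ART effects would be missed, nor that the binary outcomes are wrong for the burden estimate of Aim 2b.

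**What to change.** In the Aim 2 outcome table (section 12.d.vii):

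- Add PHQ-9 total and SNAP-IV total (or subscale) scores as HEU versus HUU outcomes. Analyse them by a mean-based GLM with robust standard errors clustered by site, not by a rank test.
- Keep moderate-severe PHQ-9, positive SNAP-IV and MINI-KID diagnoses for the burden estimate, and report their relative risks alongside.
- In the effect-size table, state the detectable score difference for the numbers expected in each tool's age range. The 0.29 SD figure applies only at 1000:100; with even ages it is about 0.42 SD for PHQ-9 and 0.22 SD for SNAP-IV.
- Reconcile the 2- to 3-fold sentence with the ADHD row, and recheck the depression row.

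The cost is a change of wording, since the tools are already administered. The drawback is that a mean symptom difference is less clinically direct than a relative risk of a disorder.
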